#### **9.7.1. Imputation for Missing Data**

No imputation of missing values is planned for this study. Missing or partially missing dates will be imputed as described in [6.4.4](#).

## **10. EFFICACY**

### **10.1. General Considerations**

The results of this study will be reported using summary tables, listings, and figures (TLFs), as appropriate. Continuous variables will be summarized using descriptive statistics: sample size (n), mean, standard deviation (SD), or coefficient of variation (CV %) as appropriate, median, interquartile range, minimum and maximum. Categorical variables will be summarized by presenting the number (frequency) and percentage in each category.

### **10.2. Testing Statistical Assumptions Including Comparability at Baseline**

The statistical assumptions of ANCOVA are:

- Normally distributed response
- Homogeneity of variance
- Independence and linear relationship between the dependent variables and the covariates
- Homogeneity of regression slopes

These assumptions will be assessed using boxplots, Q-Q plots, and scatter plots with regression lines for each treatment group. If interaction between the independent variables is suspected, interaction terms will be tested in the regression model. The additional assumption of random independent samples is insured by the use of a randomized, double-blind experimental design.

Comparability at Baseline will be assessed by comparison of treatment groups for the Baseline values using ANCOVA or Fisher's Exact Test. Potentially important imbalances between treatment groups will be assessed for their impact on efficacy analysis by including them as covariates in a linear mixed model and possible supportive sub-group analyses, as appropriate.

Patients will be randomized to treatment group stratified by developmental status.

Comparability of strata will be assessed by comparison of strata within treatment groups using ANCOVA and Fisher's exact test. If significant differences in the efficacy endpoints are found between strata, a stratified analysis will be performed. Otherwise, data from each strata will be pooled and presented as overall differences between treatment groups.

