### **Efficacy Analyses**

The ITT Population will be used for all efficacy analyses.

- For the primary endpoint, a 2-sided Type I error rate of 0.05 will be used.
- For the secondary efficacy endpoints, to maintain the trial-wise Type I error rate at 0.05, False Discovery Rate multiple comparisons correction will be used.
- For endpoints that are continuous in nature, the number of observations, mean, median, minimum and maximum, and standard deviation (SD) values will be presented as descriptive statistics. For inferential statistics, a t-test or ANCOVA will be used to compare treatment to placebo group.
- For endpoints that are categorical in nature, frequency, counts, and percentages will be presented as descriptive statistics, and Fisher's exact test, Cochran-Maentel-Haenzel, or logit model will be used for inferential statistics as appropriate.

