### **10.3. Statement of the Null and Alternate Hypotheses**

#### **10.3.1. Primary Efficacy Endpoint**

The primary efficacy endpoint in this study is:

- Percent of patients who are considered complete responders, defined as complete resolution of spasms and hysarrhythmia or a pattern of epileptic encephalopathy

confirmed by 24-hour video-EEG from Day 13 to Day 14, as determined by the Independent Central Reader.

*Null hypothesis: There is no difference in the percent of patients defined as complete responders between treatment groups.*

*Alternative hypothesis: Treatment groups have significantly different percent of complete responders.*

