##### **10.6.1. Primary Efficacy Analysis**

The primary efficacy endpoint in this study is:

- Percent of patients who are considered complete responders, defined as complete resolution of spasms and hypsarrhythmia or a pattern of epileptic encephalopathy.

The percent of complete responders will be calculated for each treatment group and compared using Fisher's exact test.

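### SAP 10.2 picks covariates for its supportive adjusted analysis from between-arm baseline comparisons and enters them in a linear mixed model that does not suit binary endpoints

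*SAP*

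**What the plan says.** SAP 10.2 sets out the assumptions of ANCOVA and then gives a baseline rule: "Comparability at Baseline will be assessed by comparison of treatment groups for the Baseline values using ANCOVA or Fisher's Exact Test". The next sentence acts on the result: "Potentially important imbalances between treatment groups will be assessed for their impact on efficacy analysis". The means is "by including them as covariates in a linear mixed model", with supportive subgroup analyses as a further possibility. The section gives no list of covariates, no threshold for an important imbalance, no endpoint, no random effect and no repeated measure.

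Other places bear on this rule:

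- **SAP 10.3.1, 10.6 and 10.6.1.** The primary endpoint is one yes/no result per patient, "confirmed by 24-hour video-EEG from Day 13 to Day 14, as determined by the Independent Central Reader". It is analysed on the ITT population: "The percent of complete responders will be calculated for each treatment group and compared using Fisher's exact test".
- **SAP Technical Summary Report, Efficacy Analyses.** For categorical endpoints the choices are Fisher's exact test, Cochran-Mantel-Haenszel (CMH), "or logit model will be used for inferential statistics as appropriate".
- **Protocol 8.4.** Logistic regression is an option for relating several variables to response, if enrolment allows.
- **Protocol 8.4.1.3.** Demographic and baseline characteristics are summarised descriptively, and formal statistical analysis of them is excluded.
- **SAP 1.** Decisions on the final analysis are to be settled before database lock, which the SAP equates with unblinding.
- **SAP 3.1 and 4.1; protocol 4.2 and 7.1.** The SAP stratifies randomisation by developmental impairment and records that risk at screening. The protocol describes permuted blocks without strata, and its screening list has no such item.

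**The concern.** In a randomised trial a baseline difference between arms arises by chance. Testing it tests a null hypothesis already known to be true, and the result says nothing about whether the variable predicts response. A strongly prognostic variable that happens to be balanced would be left out. An irrelevant one that happens to differ would go in.

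The choice also cannot be made until patients are grouped by treatment, which sits badly with SAP 1. If the primary result is close, the adjusted analysis will be used to support or question it. At that moment a reader needs to know that its covariates and form were fixed beforehand, and here they were not.

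The second problem is the model. A linear mixed model needs a continuous response and a source of correlation, such as repeated visits or clusters. Complete response has one binary value per patient, and the SAP names no cluster.

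**Working it through.** **1. The plan's own figure.** The plan attaches no figure to this rule. The design used in step 4 is the SAP's, so its power statement (SAP 3.3: 120 and 60 patients, 62% against 40%, two-sided 0.05) was checked first.

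- Pooled rate = (60 × 0.40 + 120 × 0.62)/180 = 98.4/180 = 0.5467.
- SE under the null = √(0.5467 × 0.4533 × (1/60 + 1/120)) = 0.0787.
- SE under the alternative = √(0.40 × 0.60/60 + 0.62 × 0.38/120) = 0.0772.
- Power = Φ((0.22 − 1.96 × 0.0787)/0.0772) = Φ(0.851) = 80.3%, against 80% stated.

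**2. Chance of a spurious imbalance.** SAP 9.1 lists nine items: age, sex, race and ethnicity; length, weight, BMI and head circumference; and the video-EEG results. Two assumptions are added that the SAP does not make: a 0.05 cut-off and independent variables. Then P(at least one) = 1 − 0.95^k.

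| Variables compared (k) | P(at least one) |
|---|---|
| 5 | 23% |
| 9 (SAP 9.1) | 1 − 0.6302 = 37% |
| 10 | 40% |
| 15 | 54% |

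The body-size measures are correlated, and BMI is calculated from two of the others, so independence does not hold and the true figure would differ. The video-EEG item covers several variables, so the count could exceed nine.

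**3. Does the model fit a single binary outcome?** With one observation per patient and a patient random effect, the residual variance is σ²(patient) + σ²(error). Only the sum can be estimated, so the random effect has no content. A site effect would be possible (the SAP expects about 35 sites), but none is named. Without a random effect the model is ordinary linear regression on a 0/1 outcome, and its fitted values can leave the range 0 to 1.

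**4. Does the selection rule harm the error rate?** A null simulation used 120 and 60 patients, a 40% response rate at average covariate values, and 4,000 runs per scenario. It assumed ten independent baseline variables, two of them prognostic with a log-odds slope of 0.8 or 1.2 per SD, and selection at p < 0.05. An ordinary linear model stood in for the mixed model, because no random effect is defined.

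| Result | Slope 0.8 | Slope 1.2 |
|---|---|---|
| At least one covariate selected | 39% | 41% |
| Type I error, linear model, selected covariates | 4.7% | 4.3% |
| Type I error, logistic model, selected covariates | 4.7% | 4.2% |
| Type I error, Fisher's exact test | 4.0% | 3.6% |
| Smaller of the Fisher and selected-linear p-values | 5.4% | 5.0% |
| Linear model with both prognostic covariates: some fitted value outside 0 to 1 | 98% | 100% |

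The simulation error near 5% is √(0.05 × 0.95/4000) = 0.34 percentage points. Selection did not raise the type I error above 5%. Even choosing the better of two p-values stayed within about one standard error of 5%. The unsuitable fitted values did appear, in nearly every run.

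**5. Sections side by side.** SAP 10.2 tests baseline differences; protocol 8.4.1.3 excludes formal analysis of them. SAP 10.2 adjusts with a linear mixed model; the SAP's own summary and protocol 8.4 point to CMH, logit or logistic methods for a categorical outcome.

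**The case against.** A reader might infer that the SAP uses the wrong model for its primary endpoint. The documents do not support that. The primary comparison is fixed as an unadjusted Fisher's exact test. The mixed model is an assessment of impact across efficacy analyses and is not tied by name to complete response. The section's opening on ANCOVA assumptions suggests that continuous outcomes were in mind. Repeated CGI-I scores (SAP 4.3 has the scale completed at Weeks 6, 10 and 13, and SAP 10.7.1 summarises it by visit) are one place where such a model could apply, although the SAP does not say so.

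A reader might also infer that covariates enter when a baseline p-value falls below 0.05. The text sets no such rule. Where this section means significance it says so, as in its rule on strata: "If significant differences in the efficacy endpoints are found between strata, a stratified analysis will be performed". Selection by p-value is an inference from the order of two sentences.

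A third tempting inference is that the rule inflates type I error. The simulation did not show this.

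These objections stand and limit the point. They do not remove it. By p-value or by judgement, covariates are chosen after the arms have been compared, and no list exists. Because the rule covers efficacy analysis in general and excludes no endpoint, it reaches the binary endpoints by default.

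The SAP cites protocol V2.0 of 30 October 2017, and its sample size differs from that of the protocol reviewed here (180 against 190). Some of the disagreement between the two documents may therefore come from versions. It still has to be resolved.

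**Conclusion.** The point holds for the supportive adjusted analysis only, and it is minor. SAP 10.2 lets between-arm baseline comparisons decide the covariates, against protocol 8.4.1.3 and in tension with SAP 1. It also names a model that does not suit binary endpoints and disagrees with methods listed elsewhere in the documents.

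The 37% indicates how often a chance imbalance could steer the model. It is conditional on the assumed cut-off, independence and a count of nine, and does not measure harm to inference. The cost is an adjusted result whose content cannot be known beforehand. The finding of no error inflation rests on the simulated scenarios, with ten independent variables and two prognostic ones.

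**What to change.** 1. **Reconcile stratification first.** Decide whether randomisation is stratified by developmental impairment and whether that risk is recorded at screening. Bring SAP 3.1 and 4.1 and protocol 4.2 and 7.1 into line. The covariate in item 3 depends on this.
2. **Delete the baseline tests** in SAP 10.2 and summarise baseline descriptively, as protocol 8.4.1.3 already says.
3. **Replace the linear mixed model for binary endpoints** with one pre-specified supportive logistic regression (or CMH analysis) of response on treatment and the developmental-impairment stratum. With the regression, add any further covariate that the sponsor names before unblinding. Age is an example only: neither document calls it prognostic or names it for adjustment. If it is used, take it in months as in SAP 9.1, because the age formula in SAP 6.2 returns whole years.
4. **Keep ANCOVA for continuous endpoints.** If a mixed model is wanted for repeated scores, name the endpoint, the visits and the random effect.
5. **Label any imbalance-driven model exploratory.**

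With the stratum fixed in the supportive model, the rule in SAP 10.2 and 10.4 that lets outcome differences between strata decide whether to stratify should be revised in the same edit.

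The cost is SAP wording and one supportive model, with no change to the sample size. If developmental risk is kept and the current protocol does not collect it, the reconciliation in item 1 also means a protocol and case report form change.

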## 1. INTRODUCTION

The purpose of this statistical analysis plan (SAP) is to describe the planned analyses and data displays to be included in the Clinical Study Report (CSR) for [Protocol INS011-16-082](#).

Protocol Revision Chronology:		
INS011-16-082	30 Oct 2017	V2.0

This SAP was developed per guidance documents ICH E9, Statistical Principles for Clinical Trials-v1.0. and ICH E9(R1): Addendum to Statistical Principles for Clinical Trials Final Concept Paper.

All decisions regarding final analysis, as defined in this SAP, will be made prior to Database Lock (unblinding) of the study data. Further information can be found in the protocol.

The statistical analysis plan (SAP) is based on:

- Protocol No. INS011-16-082, dated October 30, 2017.
- ICH guidelines E4 and E9 (Statistical Principles for Clinical Trials).
- Discussions with the FDA.

The purpose of this document is to provide details on study populations and on how the variables will be derived, how missing data will be handled as well as details on statistical methods to be used to analyze the safety and efficacy data for Study Protocol No. INS011-16-082.

The document may evolve over time, for example, to reflect the requirements of protocol amendments or regulatory requests. However, the final SAP must be finalized, approved by the Sponsor, and placed on file before the database is locked. Deviations from the final approved plan will be noted in the clinical study report.

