### 3. STUDY DESIGN

#### 3.1. Summary of Study Design

This is a Phase 3, double-blind, placebo-controlled, randomized, multicenter study to evaluate the efficacy, safety, and tolerability of Cannabidiol Oral Solution (CBD) as adjunctive therapy with Vigabatrin as initial therapy, compared to Vigabatrin alone in the treatment of infants newly diagnosed with Infantile Spasms (IS). Randomization will be stratified by developmental impairment (high or low) as determined by the investigator during Screening Visit 1 and then allocated to one of two treatment groups:

- Treatment with Vigabatrin plus
  - CBD 40 mg/kg/day, or
  - Matching CBD 40 mg/kg/day placebo

One hundred eighty patients in total will be enrolled into one of the two treatment arms: 120 patients in the investigational product arm and 60 patients in the placebo arm. Patients will be dosed approximately every 12 hours with food.

Study participants will be newly diagnosed pediatric patients age 3 to 12 months (inclusive) experiencing infantile spasms who satisfy all inclusion/exclusion criteria. This study will be comprised of five periods: Screening, Initial Treatment, Extended Treatment, Taper, and Follow-up Periods, with a maximum duration of approximately 137 days.

Each newly diagnosed patient with Infantile Spasms will complete a Screening Period for up to 14 ( $\pm$  5) days.

Patients will have an overnight, minimum of a 9-hour video-EEG that includes at least one full sleep-wake cycle during their Screening Visit to establish their baseline level of infantile spasms and hypsarrhythmia or a pattern of epileptic encephalopathy, and a 24-hour video-EEG at Visit 4 (Day 13) of the Initial Treatment Period to establish their final level of infantile spasms and hypsarrhythmia. During the Extended Treatment Period, a 9-hour video-EEG will be conducted to confirm parent/caregiver report of relapse or resolution.

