### **9.2. Medical History and Medical Conditions Present at Entry**

Medical and surgical history will be coded using the MedDRA, version 20.0 or above, and will be summarized by system organ class and preferred term for the Safety Population.

Development will be summarized as ‘high’ or ‘low’ risk of developmental impairment as defined by the International Collaborative Infantile Spasms Study (ICISS) for the Safety Population. ICISS criteria include the presence or absence of the following factors that increase the risk of developmental impairment: chromosomal abnormality or clinical syndrome, neonatal encephalopathy with seizures, and cerebral palsy or developmental impairment diagnosed before onset of spasms.

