#### **10.4. Subgroup Analyses**

No subgroup analysis is planned. However, if significant differences in efficacy endpoints are observed between developmentally normal vs. delayed patients, stratified analysis will be performed.

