#### **10.6.2. Presentation of the Primary Efficacy Results**

Percent of patients considered complete responders in each treatment group will be reported in a table. The p-value for difference between groups will be presented.

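### SAP 10.2 and 10.4 let observed outcomes decide whether the primary Fisher test gives way to a stratified analysis, without fixing the trigger, the test or the primary p-value, and the SAP and protocol differ on stratification

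*SAP*

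**What the plan says.** **Primary test.** SAP 10.6.1: "The percent of complete responders will be calculated for each treatment group and compared using" Fisher's exact test. The SAP's Technical Summary Report (TSR) says the same. Neither includes a stratification term.

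**Randomisation in the SAP.** SAP 3.1: "Randomization will be stratified by developmental impairment (high or low) as determined by the investigator during Screening Visit 1". The TSR and SAP 10.2 also describe stratified randomisation.

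**The switch.** SAP 10.2: "Comparability of strata will be assessed by comparison of strata within treatment groups", using ANCOVA and Fisher's exact test. Then: "If significant differences in the efficacy endpoints are found between strata, a stratified analysis will be performed"; failing that, the strata are pooled. SAP 10.4 plans no subgroup analysis but repeats the condition: "if significant differences in efficacy endpoints are observed between developmentally normal vs. delayed patients, stratified analysis will be performed".

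**Reporting.** SAP 10.6.2: "The p-value for difference between groups will be presented". It does not say from which test.

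**Methods on offer.** For categorical endpoints in general, the TSR lists Fisher's test, CMH or a logit model, to be used as appropriate. It links none of them to the switch.

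**Stratum wording.** SAP 9.2 summarises high or low "risk of developmental impairment as defined by the International Collaborative Infantile Spasms Study (ICISS) for the Safety Population", which can be read together with 3.1. But 10.4 contrasts normal with delayed patients, and 10.7.2 refers to developmental stage.

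**Protocol.** The SAP rests on Protocol V2.0 of 30 October 2017. In the current protocol, 4.2 describes permuted blocks and names no stratum, and the screening list in 7.1 has no developmental item (SAP 4.1 has one). The synopsis and 8.4.3.1 use chi-square. Protocol 4.3 mentions a randomisation schedule per centre but does not call centre a stratum.

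**The concern.** The primary p-value should come from one test fixed in advance. Here the test depends on a preliminary look at the efficacy endpoints, by stratum and, under 10.2, within arm, so the look needs unblinded outcomes. SAP 1 states: "All decisions regarding final analysis, as defined in this SAP, will be made prior to Database Lock (unblinding) of the study data". A complete rule written in advance could meet that. This one leaves the trigger level, the stratified test and the status of the resulting p-value to be settled with the data in view. Two analysts could follow the SAP faithfully on the same data and report different primary results.

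There is also a mismatch of design and analysis. If randomisation is stratified, the stratum belongs in the primary analysis by default. If it is not, as the current protocol's silence may indicate, the switch rests on a design feature that the trial lacks.

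**Working it through.** **Inputs from the documents.** 120 vs 60 patients, 62% vs 40%, two-sided 0.05, stated power 80% (SAP 3.3); Fisher's test for the primary endpoint (10.6.1); strata compared by Fisher's test within arms (10.2).

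**Assumptions in neither document.** Two strata of equal size, balanced by arm (60/60 active, 30/30 control); control rates of 40% plus or minus half the gap; a common odds ratio set so that the overall active rate is 62%; trigger at p ≤ 0.05; CMH as the stratified test.

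**Step 1: reproduce the SAP's 80%.** Pooled rate = (120 × 0.62 + 60 × 0.40)/180 = 98.4/180 = 0.5467.
- Null SE = √[0.5467 × 0.4533 × (1/120 + 1/60)] = 0.0787.
- Alternative SE = √[0.62 × 0.38/120 + 0.40 × 0.60/60] = 0.0772.
- z = (0.22 − 1.96 × 0.0787)/0.0772 = 0.85, so power is 80.3%.

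The stated figure reproduces with the pooled chi-square formula. Exact power is 80.4% for chi-square and 77.3% for the Fisher test the SAP names.

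**Step 2: the stratified test.** For stratum k with n_Ck control and n_Tk active patients, N_k in total and m_k responders, of whom a_k are controls:
- CMH = [Σ(a_k − n_Ck·m_k/N_k)]² / Σ[n_Ck·n_Tk·m_k(N_k − m_k)/(N_k²(N_k − 1))], referred to chi-square on 1 df.
- The corrected form subtracts 0.5 from the absolute sum before squaring.

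**Step 3: exact enumeration of all outcomes (%).** The main reading switches to uncorrected CMH if either arm triggers. The four readings cross either-arm or both-arm trigger with CMH uncorrected or corrected. Type I error uses an overall rate of 40% in both arms.

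| Gap in control response (points) | 0 | 10 | 20 | 30 | 40 |
|---|---|---|---|---|---|
| Power, Fisher | 77.3 | 77.4 | 77.7 | 78.4 | 79.3 |
| Power, unstratified chi-square | 80.4 | 80.5 | 80.9 | 81.5 | 82.5 |
| Power, uncorrected CMH fixed in advance | 80.4 | 80.6 | 81.7 | 84.0 | 86.9 |
| Rule changes the Fisher conclusion (main reading) | 0.2 | 0.7 | 2.9 | 5.5 | 7.6 |
| Four readings do not all agree | 0.2 | 0.8 | 2.8 | 4.5 | 4.3 |
| Type I error, either-arm trigger, uncorrected CMH | 3.95 | 4.08 | 4.58 | 4.93 | 4.97 |
| Type I error, both-arm trigger, uncorrected CMH | 3.89 | 3.81 | 3.78 | 4.15 | 4.65 |

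With corrected CMH the rule's type I error is 3.2% to 3.9%.

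**Step 4: reading the table.** At gap 0 the 3.1-point advantage of CMH over Fisher (80.4 − 77.3) reflects Fisher's conservatism, because unstratified chi-square also reaches 80.4%. The gain from stratifying itself is CMH minus chi-square: 80.4 − 80.4 = 0.0 at gap 0, rising to 86.9 − 82.5 = 4.4 points at gap 40. With uncorrected CMH and balanced strata, every changed conclusion moves towards significance. That direction is not assured for other choices: comparing the two tests as fixed alternatives, Fisher alone is significant in 2.2% of trials against corrected CMH at gap 0.

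**The case against.** **The SAP does offer stratified methods.** The TSR lists CMH and a logit model. This stands, so it would be wrong to say that no stratified method appears. The charge is narrower: the list is general, and nothing says which entry applies once the rule fires.

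**A difference in one arm may be enough.** The wording of 10.2 can fairly be read that way, so a one-arm difference is not clearly a case the rule omits. The main reading above therefore uses an either-arm trigger. With uncorrected CMH fixed, either-arm and both-arm readings differ in only 0.2/0.7/2.0/2.1/0.8% of trials across the five gaps. Much of the spread among the four readings comes from the continuity correction.

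**Version lag explains much of the mismatch.** SAP 1 names V2.0, allows the plan to evolve with amendments and requires it to be final before lock. Chi-square against Fisher, and stratified against not, may share that cause. This stands for the mismatch. It does not remove the switch, which would survive an update of version, sample size and visit days.

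**Stronger readings the documents do not support.**
- A reader might infer an inflated type I error. But 10.2 is an either/or rule, 10.5 plans no multiple comparisons for the primary endpoint, and no section permits reporting the smaller of two p-values. With CMH the rule stays at or below 5.0%.
- A reader might infer that the protocol dropped stratification. Protocol 4.2 is only silent, and 4.3 leaves centre schedules possible.
- A reader might take the 3.1% to 7.6% disagreement between Fisher and uncorrected CMH as the rule's effect. That compares two fixed tests; at gap 0, Fisher and unstratified chi-square also disagree in 3.1% of trials.

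**Conclusion.** The point holds as an incompletely specified primary analysis, and it should be corrected before database lock. An outcome-dependent rule can replace the named primary test, and it lacks a trigger level, a linked test and a statement of which p-value counts. Under the stated assumptions it changes the Fisher conclusion in 0.2% to 7.6% of trials, and reasonable readings of it fail to agree in 0.2% to 4.5%. These sizes depend on stratum shares and response gaps that neither document gives, and stratified methods other than CMH are not covered. The textual defect needs none of these figures. No error inflation is shown. Whether the trial is stratified, and by what, cannot be settled from the documents.

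**What to change.** 1. Settle whether randomisation is stratified, and by what: developmental status, centre or neither. Make the SAP TSR, 3.1 and 10.2 agree with Protocol 4.2.
2. **If stratified by developmental status:** use one stratum definition in SAP 3.1, 9.2, 10.4 and 10.7.2, and add it to Protocol 4.2 and the 7.1 screening list. Name one primary test in SAP 10.6.1, the TSR, the protocol synopsis and Protocol 8.4.3.1: a two-sided CMH test at 0.05 stratified by the randomisation factor, without continuity correction (or another stated choice). Keep the unstratified test as a sensitivity analysis.
3. **If not stratified:** delete stratification from the SAP and name one unstratified primary test in both documents. The protocol already names chi-square.
4. **Either way:** delete the outcome-dependent switch in SAP 10.2 and 10.4. State in 10.6.2 that the p-value comes from the 10.6.1 test. Bring the TSR's general list of categorical methods into line. Say whether the secondary responder tests in the TSR and SAP 10.7.1 follow the same choice.

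Cost: SAP wording and no extra patients. The stratified option also needs a protocol amendment and one screening item. If the randomisation schedule was already generated without strata, take option 3.
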